12.2 Sample size calculation

Assuming the expected proportion of patients with at least one serious/not serious adverse event surely or possibly related to JPS will be 3 %, 30 subjects (considering the case the each patient contributes for only one JPS implant) was calculated to be the sample size of this study so that the upper limit of the 95 % confidence interval for the primary endpoint, based on the exact binomial method, is under 15 %.

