12.5 Interim Analysis

An interim analysis, not planned at the start of the study, will be performed after at least 20 subjects will be enrolled and completed the "Bone Consolidation" event.

The aim of this interim analysis is to verify the consistency of testing hypothesis and to confirm the historical data on the medical device safety and performance. Interim results will be used to prepare the Clinical Evaluation Report (CER).

To preserve the integrity of the study results interpretation, a correction for multiplicity due to two planned analyses (interim+final) will be implemented using the approach proposed by O'Brian-Fleming for sequential design. (*Shein –Chung Chow et Al Sample size calculations in Clinical Research 2003, Christopher Jennison et Al Group Sequential Methods with applications to clinical Trials, 2000*)

For this purpose, sample size will be recalculated using this approach (all details are reported in the cited bibliography):

- The initial sample size will be correct by factor 1.008 for a two-sided test at 5% level and 80% power. The final sample size is $30*1.008=30.2$
- The probability level will be correct by factor 1.977, at interim the P value will be 0.0052 while at the final analysis P value will be 0.048. The corresponding confidence limits will at interim 99.5% and at final analysis 95.2%

In conclusion, applying the O'Brian-Fleming approach to control the type I error no great impact on sample size is observed and integrity of clinical study is preserved from any interpretation bias.

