14 STATISTICAL ANALYSIS METHODS

The methods of analysis to be used for both objectives of the study and for description of the study variables are detailed below.

Quantitative variables will be described with measures of central tendency and dispersion: mean, median, SD (standard deviation), Q1 (first quartile) and Q3 (third quartile), minimum and maximum. Qualitative variables will be described using absolute and relative frequencies.

In the descriptive analysis of qualitative variables, two percentage columns will be presented, total percentage (%) and valid percentage (% valid), that are respectively, the percentage over the sum of valid responses plus missing values and the percentage over the total of valid responses.

For independent samples, parametric (t-test) or non-parametric (Mann-Whitney) statistical tests will be performed, depending on the distribution of the sample.

These tests will be used in all bilateral cases and with a level of significance of 0.048. In cases where a p-value less than 0.048 appears, it refers to the existence of statistical significance.

Clopper-Pearson confidence intervals will be shown at 95.2%.

Data will be analysed using SPSS v29.0.

An interim analysis, not planned at the start of the study, was performed after at least 20 subjects will be enrolled and completed the “Bone Consolidation” event.

The aim of this interim analysis was to verify the consistency of testing hypothesis and to confirm the historical data on the medical device safety and performance. Interim results were used to prepare the Clinical Evaluation Report (CER).

To preserve the integrity of the study results interpretation, a correction for multiplicity due to two planned analyses (interim+final) was implemented using the approach proposed by O'Brian-Fleming for sequential design (Shein –Chung Chow et Al Sample size calculations in Clinical Research 2003, Christopher Jennison et Al Group Sequential Methods with applications to clinical Trials,2000)

For this purpose, sample size was recalculated using this approach (all details are reported in the cited bibliography):

- The initial sample size was correct by factor 1.008 for a twosided test at 5% level and 80% power. The final sample size is $30 * 1.008 = 30.2$
- The probability level was corrected by factor 1.977, at interim the P value was 0.0052 while at the final analysis P value will be 0.048.

The corresponding confidence limits were at interim 99.5% and at final analysis 95.2%

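### The 80% power quoted in the interim section has no basis, because the base size of 30 comes from an interval target and not from a powered test

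*Protocol*

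**What the plan says.** Protocol 12.2 sets the size in one step. It begins "Assuming the expected proportion of patients with at least one serious/not serious adverse event surely or possibly related to JPS will be 3" per cent, and then states that "30 subjects (considering the case the each patient contributes for only one JPS implant) was calculated to be the sample size of this study". The criterion is that the upper 95% limit, "based on the exact binomial method, is under 15" per cent. The synopsis and SAP section 9 give the same derivation and add a 10% dropout rate and a ceiling of 40 implant cases. Protocol 12.1 supplies the 15%, which is the top of the literature range of 5.1% to 15.0%, and describes the limit as a device for sizing.

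Protocol 12.5 adds an interim look, which "will be performed after at least 20 subjects will be enrolled and completed" the bone consolidation event. It then adjusts the size: "The initial sample size will be correct by factor 1.008 for a two-sided test at 5% level and 80% power". The result is given as 30.2. The synopsis repeats this, and SAP section 14 puts it in the past tense: "The initial sample size was correct by factor 1.008 for a twosided test at 5% level and 80% power". The accompanying nominal levels are "at interim the P value will be 0.0052 while at the final analysis P value will be 0.048", and the final interval becomes 95.2%. All three places conclude that the interim hardly affects the sample size.

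On the form of the interval, Protocol 12.3.2 asks for both an upper and a lower limit by the Clopper method, and SAP section 14 specifies Clopper-Pearson at 95.2%.

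**The concern.** An O'Brien-Fleming inflation factor preserves the power of a fixed-sample test that has already been sized for that power. The 30 in Protocol 12.2 was not sized that way: it comes from where an exact upper limit falls at an expected rate. Section 12.5 nevertheless describes the quantity being inflated as belonging to an 80% power design.

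What is at stake is how the primary safety result is read. Someone who believes the study had 80% power may treat an upper limit above 15% as an unexpected and informative result about the device. If the actual probability of staying at or below 15% is well under 80%, such a result can be quite likely even when JPS performs exactly as assumed.

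**Working it through.** **Inputs.** Expected rate 3% and size 30 (Protocol 12.2). Limit of 15% and range 5.1% to 15.0% (Protocol 12.1). Two-sided Clopper interval (Protocol 12.3.2), at 95.2% for the final analysis (Protocol 12.5, SAP 14). Factor 1.008 and nominal levels 0.0052 and 0.048 (Protocol 12.5). Cap of 40 implant cases and 10% dropout (synopsis, SAP 9).

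**Step 1: the plan's inflation step reproduces.** Two equally spaced O'Brien-Fleming looks at two-sided 5% give a constant of 1.977, nominal levels of 0.0052 and 0.0480, and an inflation factor of 1.0078 at 80% power. Then 30 × 1.008 = 30.24, which as a number of subjects is 31.

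**Step 2: the base size of 30.** The Clopper-Pearson upper limit for x events in n is the (1 − a) quantile of Beta(x + 1, n − x), with a = (1 − level)/2 if two-sided and a = 1 − level if one-sided. The expected count is 0.03 × 30 = 0.9, so 1 event is the nearest whole number.

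- Two-sided 95%: 0/30 gives 11.6%; 1/30 gives 17.2%. With 1 event, 35 subjects are needed to get under 15%.
- Two-sided 95.2%: 0/30 gives 11.69%; 1/30 gives 17.35%; 1/35 gives 15.04%. With 1 event, 36 are needed.
- One-sided 95%: 1/30 gives 14.9%, and 30 is the smallest size that works with 1 event.

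So 30 reproduces only with a one-sided 95% limit, which is not the interval the documents describe. With the two-sided interval, 30 meets the target only if no event occurs.

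**Step 3: probability of an upper limit of at most 15% at a true 3%.** Let k be the largest count that passes. The probability is P(X ≤ k) for X binomial (n, 0.03). For the two-sided 95.2% interval, with n counting subjects and one implant each:

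| n | Largest count that passes | Probability |
|---|---|---|
| 30 | 0 | 0.97^30 = 40.1% |
| 31 | 0 (1/31 gives 16.83%) | 0.97^31 = 38.9% |
| 36 | 1 (1/36 gives 14.64%) | 0.97^36 + 36 × 0.03 × 0.97^35 = 70.6% |
| 40 | 1 (2/40 gives 17.03%) | 0.97^40 + 40 × 0.03 × 0.97^39 = 66.2% |
| 46 | 2 | 84.1% |
| 55 | 2 | 77.2% |
| 56 | 3 | 91.3% |

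At 30 the figure is 40.1% at the 95% level too, because again only 0/30 passes. The probability falls as n grows until one more event is allowed. That is why 80% is first reached at 46, lost again by 55, and held only from 56. The best value within the cap is 70.6% at 36, which is also 40 less 10% dropout.

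For the one-sided 95% limit at 30, k = 1 and the probability is 0.97^30 + 30 × 0.03 × 0.97^29 = 77.3%. On that reading 80% is first reached at 40 (k = 2, 88.2%).

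**Step 4: does the cost of the interim depend on the 80%?** With equal spacing, the factor is 1.008 at 80% power and 1.010 at 40%. The second gives 30 × 1.010 = 30.3, again 31 subjects.

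**The case against.** Four points can be made for the plan, and each stands at least in part.

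- **The arithmetic is right.** A reader might infer that 1.008 or 30.2 is a calculation error. It is not: the factor and the product are correct for two equally spaced looks. The 80% is used to choose the factor and is not reported as a computed property of this design, so it is better called unsupported than miscalculated.
- **The interim costs little.** A reader might infer that the plan's conclusion about sample size collapses without the 80%. It does not. Step 4 gives 31 at either power, and moving from 95% to 95.2% leaves the passing count at 30 unchanged. The planned look after at least 20 subjects is not at half of 30, but that is a separate matter. At 20/30 the factor would be about 1.017, and 30 × 1.017 = 30.51 is still 31.
- **The 15% limit is a planning target.** Protocol 12.1 introduces it for sizing, Protocol 12.4 assesses the hypothesis by descriptive statistics, and neither document states a pass/fail rule for the final interval. The probabilities above therefore hold only if the target is used as the criterion. An exact upper limit of at most 15% does correspond to a test against 15%, so what is missing is the power, not every element of a test.
- **40.1% is not the only figure.** It belongs to exactly 30 subjects and a two-sided limit. More subjects or a one-sided limit raise it.

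None of this supplies a basis for 80% at 30: the two readings give 40.1% and 77.3%.

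**Conclusion.** The concern holds in limited form, at moderate severity. The 80% power in Protocol 12.5, the synopsis and SAP 14 is unsupported, because the 30 to which it is attached comes from an interval target with no power calculation. If an upper limit of at most 15% is the criterion and the true rate is 3%, the probability at 30 subjects is 40.1% with the documented two-sided interval, or 77.3% one-sided at 95%. Under the two-sided 95.2% interval, 80% is not reached within the 40-case cap, even if every case is a separate subject. Under the one-sided 95% reading it is reached only at the cap itself.

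The derivation of 30 has a related fault: with the two-sided interval and 1 event, the upper limit is above 15%.

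It would go too far to say that the study has a 40% chance of success, since no success rule is laid down. It would also go too far to say that the interim adjustment is wrong or costly. No analysis, interval or enrolment limit changes, which is why the point is not rated higher.

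**What to change.** Wording changes only, with no extra patients:

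1. In Protocol 12.5, the synopsis and SAP 14, delete the reference to 80% power. Alternatively, replace it with the actual probability of an upper limit of at most 15% at a true 3%, stating the interval's level and sidedness and the assumption of one implant per subject. For the two-sided 95.2% interval: 40.1% at 30, 38.9% at 31, 70.6% at 36, 66.2% at 40.
2. In Protocol 12.2, the synopsis and SAP 9, say whether the limit is one-sided or two-sided. If two-sided, correct the statement that 30 keeps it under 15%: this is true with 0 events, but with 1 event it needs 35 at 95% or 36 at 95.2%.
3. If an inflated size is kept, give it as 31 wherever the sample size appears.
4. State that an upper limit above 15% is not by itself evidence that JPS lies outside the state of the art.

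The cost is a few sentences in the two documents and a stated probability less favourable than 80%.

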13. ETHICS AND REGULATORY REQUIREMENTS

This investigation will be performed according to the following guidelines:

- World Medical Association Declaration of Helsinki;

13.1 Regulatory Approval

Prior to the initiation of this investigation and first data collection, the CIP and all other relevant documents as required by the relevant Independent Ethics Committee/Institutional Review Board (IEC/IRB) will be submitted for review and approval.

Any amendment to the CIP will be submitted to the IEC/IRB for notification and/or approval, before implementation, as applicable.

13.2 Subject Information and Consent

The aim of the study is to collect clinical data based on medical records for patients treated with the JPS system in the past for whom follow-up assessment and JPS removal is already done (retrospective group) and for patients who has undergone JPS implantation and will have follow-up assessments and JPS removal (prospective group).

All subjects should give informed consent to participate in this study. Prior to being enrolled into the study, each patient (if he/she is adult at the time of the screening visit), or his/her parents/legal representative (if he/she is minor at the time of the screening visit), will be required to give his/her written and dated informed consent to participate the study and to collect and process their clinical data, and to anonymously store the data electronically. Also minors patients will be informed as far as possible by the investigators about the study and will be given an age dedicated informed form. Their willingness or refuse to participate to the study, if expressed, must be taken into consideration by the investigator.

Each patient/parents/legal representative will have the opportunity to discuss the informed consent with the Investigator prior to sign it. The Investigator or his/her designee will inform all patient/parents/legal representative regarding the purpose of the study and the clinical data that will be collected. The Investigator will deliberate that, considering this is an observational Study, there are no foreseeable risks resulting from study participation as well as potential benefits that may result from participating in the study.

Each patient/parents/legal representative will be informed by the Investigator that he/she is free to refuse to participate in the study and, if he/she choose to participate, that he/she may withdraw from the study at any time without providing reasons. In addition, the patient/parents/legal representative will be informed that, in some necessary cases, the Investigator may prematurely terminate their participation providing an appropriate reason.

The Investigator will provide the patient/parents/legal Representative with contact details in case they need further information after ICF signature.

Each patient/parents/legal representative will be informed that his/her medical records will be subjected to review by the Sponsor representatives, and may be subjected to review for the

auditor and regulatory authorities, and that the information will be used during the analysis of the results.

The data gathered for this group at the visits and assessment during the follow-up period, will be systematically collected by the investigator in eCRF.

Subjects will not undergo additional visits nor invasive or burdensome procedures additional to those already performed under the normal clinical practice. The scope of data collection is limited to the available data in the patients' charts.

13.3 Subject Confidentiality

All information and data sent to parties involved in study conduct concerning patients or their participation in this study will be considered confidential per the requirements of EU GDPR regulations and local requirements. The Informed Consent shall describe the process of subject data protection in details. Each JPS implant will be assigned a unique case number (ID), and reported in the eCRF. Considering that each patient can contribute for more than one JPS implant: one patient can have more than one ID. In the eCRF the IDs are linked to the first ID assigned to the same patient by the clinical site. Records of the subject/study ID number relationship will be maintained by the study center. The study ID number is to be recorded on all study documents to link them to the subject's medical records at the site. To maintain confidentiality, the subjects' name or any other personal identifiers should not be recorded on any study document other than the Informed Consent Form and the patients screening log. In the event a subject's name is included for any reason, it will be blinded as applicable.

Confidentiality of data will be observed by all parties involved at all times throughout the clinical investigation. All data shall be secured against unauthorized access. The privacy of each subject and confidentiality of his/her information shall be preserved in reports and when publishing any data.

14. STUDY MANAGEMENT AND ADMINISTRATION

14.1 Supplies

After the required approval will be obtained before the site will be initiated, the sponsor will provide the site with the following supplies:

- A paper and electronic copy of this CIP;
- Blank copies of the ICFs to be signed by the enrolled subjects;
- The Investigator Site File (ISF) containing all the study related documents;
- An eCRF platform and the credential to enter the system to upload clinical data;
- An appropriate training on study procedures and eCRF management.

14.2 Monitoring

The sponsor planned to perform a 100% source data verification (SDV), on inclusion/exclusion criteria and on the endpoints variables. On the remaining data the SDV will be performed by random spot check. Before each visit the monitors will contact the investigator/centre to schedule the visit and will send a written confirmation and the related agenda.

In order to fulfill its responsibility of assuring the proper conduct of the study regarding adherence to the CIP and the completeness and accuracy of the data recorded on the case report forms, the sponsor planned to perform at least the following monitoring visits:

- Site Initiation Visit (SIV), to be performed after EC approval;
- 6 monitoring visits throughout the life phase of the study and according monitoring plan;
- Close Out Visit (COV), after the last patient's data are entered into eCRF.

In case of need the investigational site is subjected to additional monitoring visits. The Investigator and/or study staff will be expected to be available for at least a portion of the monitoring visit to answer questions and to provide any missing information.

14.3 Direct Access to Source Data/Documents

With all efforts to ensure that patients' pseudo-anonymity and confidentiality is respected, the Investigator will permit the clinical monitors to have direct access to all study records that are the eCRF, the ISF and all the source data.

14.4 Audit

There may be a possibility that the Quality Assurance Department of the sponsor may audit the compliance to CIP procedures according to the company Standard Operating Procedures.

The investigator will permit to be audited by sponsor personnel during and after the study has been completed.

14.5 Adherence to Protocol

CIP deviations will be reported to the sponsor who will assess their significance (Major and Minor). All deviations will be reported and discussed in the clinical investigation report.

In case of a CIP amendment, before the suggested modifications will be implemented, the sponsor will notify to the relevant IEC/IRB the new version of the CIP, specifying whether the modifications are substantial/not-substantial and, if applicable, will put the study on hold until the re-approval will be obtained.

14.6 Data Handling and retention

The sponsor and the investigator assume the responsibility to assure that the clinical data will be collected according to the CIP requirements (no additional data will be collected), local laws and obligations and the World Medical Association Declaration of Helsinki. The clinical data obtained as a result of this study is considered confidential between the site and the sponsor: disclosures to third part are prohibited or, if necessary for example to perform statistical analysis with contracted vendors, will be protected by non-disclosure agreements.

Before the Site Initiation Visit, the sponsor will provide a validated eCRF system and will train the Investigators about the data entry procedures, data clearing and queries resolution. Only the data recorded in the eCRF will be considered for the statistical analysis. The clinical data entered in the eCRF must come from the source data, that is all information in original (or certified copies) patients' clinical records, records of clinical findings, investigator's observations/assessment.

The investigator assumes the responsibility to assure that the last data will be entered within 2 week from the plate removal of the last patient.

The investigator will have to keep all study related documentation for the longest possible duration, but at least for 15 years after the completion or premature termination of the study. No data should be destroyed without agreement of the sponsor. The Sponsor will maintain all documentation pertaining to the study for the lifetime of the product.

Sponsor and investigators shall take measures to prevent accidental or premature destruction of these documents and they may rely on a third part for documents retention by a non-disclosure agreement to protect data confidentiality.

14.7 Clinical Study Report

The clinical study report shall be completed by the sponsor, or a designed delegate by the means of a non-disclosure agreement, even if the clinical investigation will be terminated prematurely, only after:

- all queries concerning the eCRF will be closed;
- the database will be locked;
- the statistical report will be written and approved.

The sponsor will draft the clinical study report within 2 months after the statistical report will be finalized. That report will be reviewed and approved by the investigator and, as soon as available, shall be provided to the relevant IEC/IRB, to the regulatory authorities (when applicable). For all statistical details related to Interim Analyses please refer to section 12.5.

14.8 Insurance and Liability

No additional procedures for patients nor for the investigational team members are planned for the present observational study with respect to the normal clinical practice, that actually comprises a retrospective and prospective data collection. The sponsor, therefore, is not requested to put in place an additional dedicated liability insurance covering this study.

